Testing Ultraprocessed Front-of-Package Labels in Chile

NCT06293963

April 10th, 2025

Study Protocol and Analytic Plan

Introduction

This study aims to examine the effects of a warning label signaling that a product is ultraprocessed among a sample of Chilean parents. This document pre-specifies our planned analytic approach prior to data collection.

Study Protocol

Participants will complete an online randomized experiment programmed in Qualtrics. After providing informed consent and completing a parent study, participants will be randomly assigned into 1 of 2 arms: a control arm or an ultraprocessed warning label arm. In the control arm, products will carry only nutrient warning labels per Chile's current policy, while in the ultraprocessed warning label arm, products will carry both nutrient labels and an ultraprocessed warning label.

Participants will see three different mock bags of potato chips with the same flavor (designed to mitigate confounding by product type or flavor) displayed in a random order. All three products will be ultraprocessed. One product will not be high in any nutrients of concern, one will be high in sodium, and one will be high in sodium and saturated fat. For each product, participants will rate their purchase intentions, perceived product healthfulness, and indicate whether they believe the product to be ultraprocessed.

Hypotheses

Correct identification of UPFs (co-primary outcome): We predict that, compared to the control arm, correct identification of products as UPFs will be higher among participants in the UPF warning label arm (H1).

Purchase intentions (co-primary outcome): We predict that, compared the control arm, product purchase intentions will be lower among participants in the UPF warning label arm (H2).

Perceived product healthfulness (secondary outcome): We predict that, compared the control arm, perceived product healthfulness will be lower among participants in the UPF warning label arm (H3).

Moderation hypotheses: We predict that the impact of the UPF label on purchase intentions (H4) and perceived product healthfulness (H5) will be greater for the product not high in any nutrients of concern than for the products high in one or two nutrients of concern.

Main Analyses

We will use a two-sided critical alpha of 0.05 to conduct all statistical tests. All confidence intervals presented will use a 95% confidence level. Analyses of the primary

and secondary outcomes will include all participants according to the trial arm to which they were randomized.

For correct identification of products as UPF (dichotomous outcome), we will first descriptively report unadjusted proportions of correct identification for each product and for all three products simultaneously (i.e., whether the participant identifies all three products as UPFs nor not) in each experimental arm. To test H1, we will fit a logistic mixed-effects regression model. The model will include random intercepts to account for repeated measures within participants. The model will regress identification of products as UPFs on indicator variables for experimental arm, indicator variables for product, and their interactions. After model estimation, we will test the joint statistical significance of the interaction terms, and, if not statistically significant, we will drop the interactions from the models. Regardless of the presence of the interaction terms in the final model, we will obtain predicted probabilities of correct identification of products as UPF by experimental arm for each separate product, which we will use to conduct a joint test of statistical significance of the differences in predicted probabilities across products. If such differences are jointly significant, we will report the average differential effect (ADE) of the UPF label (i.e., differences in predicted probabilities between experimental arms) for each product. Alternatively, if these differences are not jointly significant, we will report the ADE of the UPF label across products.

For purchase intentions and perceived healthfulness (continuous outcomes), we will first descriptively report unadjusted mean scores for each product and averaged across products in each experimental arm. To test H2 and H3, we will use linear mixed-effects regression models. Models will include random intercepts to account for repeated measures within participants. Models will regress each outcome on indicator variables for experimental arm, indicator variables for product, and their interactions. After model estimation, we will test the joint statistical significance of the interaction terms. If the interactions are jointly significant, we will keep them in the model and report the average differential effect (ADE) of the UPF label (i.e., differences in predicted means between experimental arms) for each product. Alternatively, if the interactions are not jointly significant, we will drop them from the models and report the ADE of the UPF label across products. We will use complete case analysis to handle any missing data.

Sample Size and Power

This study will occur in a survey that will follow a parent experiment. The total sample of 3,300 size was calculated based on the primary outcomes of the parent study. Using G*Power3.1, we determined that the minimum effect size we would be able to detect with this pre-determined sample size. With an alpha of 0.05, 80% power, and 1 degree of freedom, we would be able to detect an effect of $d=0.06$ or larger. We concluded that this sample size would be enough, given that, on a previous study using similar labels, we found an effect size of $d=0.16$ on correct identification of products as UPF.

Exclusions and Outliers

We will exclude participants who complete the survey implausibly quickly (defined as $<1/3$ of the median completion time) and those who completed less than 90% of the survey.

Interim Analyses

No interim analyses are planned.

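### H4 and H5 predict which product shows the larger label effect, but the plan offers only a non-directional joint interaction test and no between-product contrast with a confidence interval

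*Combined protocol and SAP*

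**What the plan says.** The Hypotheses section states two moderation hypotheses, H4 for purchase intentions and H5 for perceived healthfulness. Each predicts a label effect "greater for the product not high in any nutrients of concern than for the products high in one or two nutrients" of concern. That is a directional statement about differences between products.

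For these two outcomes, the Main Analyses section says: "To test H2 and H3, we will use linear mixed-effects regression models". H4 and H5 are not mentioned again. The models contain arm, product and their interactions, with a random intercept per participant. The plan then says:

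- "After model estimation, we will test the joint statistical significance of the interaction terms".
- If they are significant, the plan will "report the average differential effect (ADE) of the UPF label (i.e., differences in predicted means between experimental arms) for each product".
- Otherwise, "if the interactions are not jointly significant, we will drop them from the models" and "report the ADE of the UPF label across products".

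The plan also reports, as description, "unadjusted mean scores for each product and averaged across products in each experimental arm". On error rates it says: "We will use a two-sided critical alpha of 0.05 to conduct all statistical tests". Any intervals presented are to be at the 95% level, but no interval for a difference between products is named.

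**The concern.** A joint interaction test asks whether the three label effects differ in any way. H4 and H5 ask something narrower: whether one named product has the largest effect.

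- **After a significant joint test**, the reader gets three within-product arm differences. Direction and ranking, which are the content of H4 and H5, are left to comparison by eye.
- **After a non-significant joint test**, the interactions disappear. No interval shows how much moderation the data exclude.
- **The hypothesis has two readings.** The effect for the no-nutrient product could have to exceed that for *each* of the other two, or only their *mean*. With no rule fixed, the verdict could be settled after the data are seen, in a document whose purpose is to prevent that.

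**Working it through.** The plan gives no power or precision figure for H4 or H5, so there is none to reproduce.

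**Inputs from the document.** Two arms and three products give (2 − 1) × (3 − 1) = 2 interaction df (derived; the plan does not print it). Total sample 3,300. Two-sided alpha 0.05.

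**Assumptions, not in the document.** Equal allocation, so n = 1,650 per arm; no exclusions; within-person correlation (ICC) of 0.3, 0.5 or 0.7; label effects as reductions in SD units, listed as no-nutrient/one-nutrient/two-nutrient.

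**Formulas.** Under the random-intercept model, the three estimated label effects are jointly normal, with variance 2/n each and correlation equal to the ICC.

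- Average contrast (no-nutrient effect minus the mean of the other two): SE = √(1.5 × (1 − ICC) × 2/n). At ICC 0.5: √(1.5 × 0.5 × 2/1650) = 0.030 SD.
- Each pairwise contrast: SE = √(2 × (1 − ICC) × 2/n). At ICC 0.5: 0.035 SD.
- Joint test: 2-df chi-square, critical value 5.99.
- *Mean* rule: average contrast z > 1.96. *Each* rule: both pairwise z > 1.96.

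95% CI half-widths at ICC 0.3, 0.5, 0.7 are 0.070, 0.059, 0.046 SD for the average contrast and 0.081, 0.068, 0.053 SD for each pairwise contrast.

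**Results** from 1,000,000 simulated trials per scenario; the powers agree with the noncentral chi-square, normal and bivariate normal formulas. Entries are % of trials at ICC 0.3, 0.5, 0.7.

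| Quantity | 0.12/0.06/0.06 | 0.15/0.05/0.05 | 0.15/0.10/0.05 |
|---|---|---|---|
| Joint test significant | 30, 41, 63 | 71, 85, 98 | 58, 73, 92 |
| *Mean* rule met | 39, 51, 73 | 80, 91, 99 | 56, 70, 89 |
| *Each* rule met | 16, 24, 44 | 53, 71, 93 | 20, 29, 45 |
| *Mean* rule met, joint test not significant | 11.3, 12.5, 11.7 | 10.3, 6.6, 1.4 | 7.8, 6.0, 2.3 |
| *Mean* rule met, *each* rule not met | 23, 27, 28 | 27, 20, 6 | 35, 42, 44 |

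1. **Direction.** With H4 reversed (0.05/0.15/0.15) the joint test is significant in 71, 85, 98% of trials, exactly as often as with H4 true at 0.15/0.05/0.05.
2. **Ranking by eye.** With 0.13/0.13/0.05 the no-nutrient effect equals the one-nutrient effect, so H4 is false on the *each* reading. The joint test is significant and the no-nutrient estimate ranks largest in about 25 to 44% of trials across the three ICCs. The *each* rule is met in about 2.5%.
3. **Loss through the gate.** Fourth row of the table: on the *mean* reading, a significant and correctly signed contrast goes unreported in 1.4 to 12.5% of trials. On the *each* reading the loss is at most 0.9%.
4. **Open reading.** Meeting both pairwise rules implies a significant average contrast, so the last row is the difference between the two powers.

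With 1,400 per arm, to allow for exclusions, the gate losses on the *mean* reading are 10.4, 11.9, 12.4% (0.12/0.06/0.06) and 11.6, 8.6, 2.7% (0.15/0.05/0.05).

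**The case against.** The plan does contain a moderation analysis. H2 and H3 alone need no interaction terms, so the joint test can fairly be read as serving H4 and H5, and an omnibus test followed by effects per product is a conventional sequence. The product-specific effects carry signs. In the reversed scenario above, given a significant joint test, the no-nutrient effect is the smallest of the three in 99.7% or more of trials, so gross reversal would be seen. With the no-nutrient product as reference, the two interaction coefficients are the required pairwise contrasts. The wording of H4 and H5 mentions no average and leans towards the *each* reading, where the gate costs almost nothing. In the graded scenario the joint test has slightly more power than the average contrast. H4 and H5 are labelled neither primary nor secondary.

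Much of this stands: the joint test may well be meant for H4 and H5, direction is visible informally, and the power argument alone is modest. But ordering point estimates is not a test, as the 0.13/0.13/0.05 case shows. The plan fixes no reference product and does not undertake to report the interaction coefficients, and it removes them when the joint test is not significant. The unadjusted means by product and arm allow a point estimate to be worked out, but no interval or test is stated for it. Leaning towards one reading is not the same as fixing it.

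**Conclusion.** The concern holds. In neither branch does the plan supply a directional test of H4 or H5, or a between-product estimate with a confidence interval, and it does not say which comparison would count as support. This rests on the text alone.

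The size of the consequence depends on the assumed sample split, correlations and effects. In the scenarios tried, the two readings disagree in about 6 to 44% of trials, and the gate suppresses a significant average contrast in 1.4 to 12.5%. If the *each* reading is intended, the gate loss is negligible; the gain is then a proper test and intervals. The plan should be changed on this point, but H1 and H2 do not depend on it.

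**What to change.** Before data collection, add to Main Analyses, for H4 and H5 separately:

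- Whether the no-nutrient effect must exceed the *mean* of the other two or *each* of them, with direction defined as a larger reduction under the label.
- That the full-interaction model is kept for H4 and H5 whatever the joint test shows.
- On the *mean* reading: one 1-df contrast, the no-nutrient effect minus the mean of the other two.
- On the *each* reading: both pairwise contrasts (no-nutrient minus one-nutrient, no-nutrient minus two-nutrient), with support claimed only if both are significant in the predicted direction.
- That every contrast is tested at the plan's two-sided 0.05 and reported with its estimate and 95% CI.

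The joint test can still decide how H2 and H3 are summarised.

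The cost is one or two sentences in the plan and one or two post-estimation contrasts per outcome, from models already being fitted, with no new data. The *each* rule has lower power than the average contrast (second and third rows of the table), so the choice should be made with that in view.

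### Random-intercept-only linear models assume equal variance and correlation across three deliberately different products, which can mis-size the H4/H5 contrast and, if variances differ, the product-specific intervals

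*Combined protocol and SAP*

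**What the plan says.** The Main Analyses section specifies linear mixed models for purchase intentions and perceived healthfulness. On the repeated ratings it says: "Models will include random intercepts to account for repeated measures within participants". The fixed part is saturated: "Models will regress each outcome on indicator variables for experimental arm, indicator variables for product, and their interactions". It states no product-specific variance, random product effect, unstructured covariance or robust standard error.

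The interaction test decides what is reported: "After model estimation, we will test the joint statistical significance of the interaction terms". If it is significant, the authors will "report the average differential effect (ADE) of the UPF label (i.e., differences in predicted means between experimental arms) for each product". If not, "we will drop them from the models and report the ADE of the UPF label across products".

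The Hypotheses section makes a prediction about the label's impact on purchase intentions (H4) and on healthfulness (H5). That impact, it says, "will be greater for the product not high in any nutrients of concern than for the products high in one or two nutrients of concern". The analysis text writes no single-degree-of-freedom contrast for this prediction. The Study Protocol section describes the three products: one high in no nutrient of concern, one high in sodium, and one high in sodium and saturated fat. All tests are two-sided at 0.05, and all intervals are at 95%.

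**The concern.** A random intercept with a common residual variance imposes compound symmetry: one variance for every product and one correlation for every pair. In the control arm, one bag carries no warning and the other two share a sodium warning. It is plausible, though not shown, that participants rate the two warned bags more alike, or that the unwarned bag's ratings have a different spread.

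H4 and H5 set the unwarned product against the other two, so their test depends directly on the within-person covariance. The product-specific ADEs depend on each product's own variance, yet the model gives all three the same standard error. At stake are the type I error or power of the moderation claims and the coverage of the product-level intervals. A larger sample does not help, because the ratio of model to true standard error does not depend on N.

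**Working it through.** **Figures in the plan.** The document gives no standard deviation, correlation, standard error or error rate for these quantities, so there is nothing of its own to reproduce. Its detectable effect of d = 0.06 does not bear on this check.

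**Inputs from the document.** Three ratings per participant, two arms, two-sided alpha 0.05, 95% intervals, and 3,300 participants in total. Complete-case analysis is stated, so near-balanced data are taken.

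**Assumptions.** All variances and correlations below are assumed. The covariance is taken to be the same in both arms. Allocation is not stated; 1:1 is used in simulation.

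**Method.** With balanced data, the random-intercept fit replaces the true covariance S by C, which has the average variance on the diagonal and the average covariance off it. For a contrast *l*:

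- SE ratio = sqrt(l′Cl / l′Sl)
- size of a nominal 5% test = 2 × P(Z > 1.96 × ratio)

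**Overall ADE**, l = (1/3, 1/3, 1/3). C and S have the same total, so the ratio is 1.000 in every case.

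**H4/H5 contrast**, l = (1, −½, −½), unit variances, unwarned-warned correlation *a*, warned-warned correlation *b*:

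- true variance ∝ 1.5 + 0.5b − 2a
- model variance ∝ 1.5 × (1 − (2a + b)/3)

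For a = 0.5 and b = 0.7, the true value is 1.5 + 0.35 − 1.0 = 0.85. The model value is 1.5 × (1 − 0.5667) = 0.65. The ratio is sqrt(0.65/0.85) = 0.874, and the size is 8.7%.

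| a / b | True | Model | SE ratio | Contrast alone | Contrast after a significant joint test, no moderation | Joint 2-df test |
|---|---|---|---|---|---|---|
| 0.5 / 0.6 | 0.80 | 0.70 | 0.935 | 6.7% | 3.4% | 5.1% |
| 0.5 / 0.7 | 0.85 | 0.65 | 0.874 | 8.7% | 4.5% | 5.4% |
| 0.6 / 0.8 | 0.70 | 0.50 | 0.845 | 9.8% | 5.1% | 5.6% |
| 0.4 / 0.8 | 1.10 | 0.70 | 0.798 | 11.8% | 6.1% | 6.2% |
| 0.7 / 0.5 | 0.35 | 0.55 | 1.254 | 1.4% | 0.6% | 5.5% |

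If H4/H5 were instead read from single arm-by-product coefficients (unwarned against one warned product), the sizes in the first three rows are 5.8%, 6.8% and 7.4%.

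**Product-specific ADEs**, l = (1, 0, 0) and so on. With equal variances the ratio is exactly 1.000 whatever the correlations. With variances 1.3, 1 and 1 the average is 3.3/3 = 1.1:

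- unwarned product: sqrt(1.1/1.3) = 0.920, coverage about 93%
- each warned product: sqrt(1.1/1) = 1.049, coverage about 96%

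With SDs of 1.2, 1.0 and 0.9, coverage is 91.1%, 95.9% and 97.7%.

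**Simulation of the remedy** (10,000 trials, 1,650 per arm, SDs 1.2/1.0/0.9, correlations 0.5/0.5/0.7). Freeing the 3x3 covariance changed the type I error as follows:

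- H4 contrast: 10.2% to 4.8%
- product ADEs: 8.4%, 3.9% and 2.3% to 5.0%, 4.8% and 5.0%
- joint test: 5.7% to 5.1%
- overall ADE: 5.1% both ways

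**The case against.** The strongest reply is that the inflated rates belong to a test the plan does not write. Its only stated moderation test is the joint one, which stays close to nominal: 5.1% to 5.6% in the main scenarios and 6.3% in the most extreme case tried (SDs 1.3/1.0/0.9, correlations 0.5/0.45/0.75). The interactions are also dropped unless that test is significant, so any H4/H5 contrast comes only after it. Under no moderation, that sequence brings rejection down to 3.4% to 5.1% in the main scenarios.

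Most of this stands. A reader might infer that the moderation hypotheses will be tested above 0.05, but the document does not support that as a fact. Two limits remain. The joint test has no direction, so it cannot by itself show a larger effect for the unwarned product; H4 and H5 as worded need a contrast or single coefficients. And the gate gives no protection if the two warned products' effects differ clearly but average to the unwarned product's effect. The joint test then passes and the contrast runs at its ungated rate, for example 8.7% at 0.5/0.7.

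It is also fair to say that the asymmetry is conjecture. The bags share a flavor, and in the label arm all three carry the ultraprocessed warning. The error is zero under compound symmetry and can run in either direction otherwise.

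**Conclusion.** The concern holds in a conditional form. The plan assumes equal variances and correlations for products that differ by design, and offers no support for this. If the assumption fails, the H4/H5 contrast can be too liberal or too conservative. Over the main assumed range it is 6.7% to 9.8% ungated and 3.4% to 5.1% gated under no moderation, and it is 1.4% ungated if the asymmetry reverses.

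Three stronger readings are tempting and not supported:

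- **That the error bars are wrong.** They may be; the document has no figures to show it.
- **That unequal correlations spoil the product-specific intervals.** They do not; only unequal variances do.
- **That the same fault is shown for H1.** The logistic model also relies on random intercepts ("The model will include random intercepts to account for repeated measures within participants"), but the closed form covers linear models with balanced ratings. Nothing here quantifies the logistic case.

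The linear-model estimates are unbiased. The overall ADEs for H2 and H3, including the co-primary purchase-intentions result, are safe with balanced ratings and either 1:1 allocation or the same covariance in both arms. This is an inexpensive improvement to the secondary inferences, not a threat to the main result.

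**What to change.** For the H2 to H5 linear models, specify an unstructured 3x3 within-participant covariance across products. Alternatively, keep the random intercept and use participant-clustered robust standard errors. State that the interaction test, the H4/H5 contrasts and the product-specific ADEs all come from that model, and write the H4/H5 contrasts out.

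The cost is a sentence or two in the analysis plan and one model option. The unstructured form has six covariance parameters, which about 3,300 participants estimate easily. Design and sample size do not change, and almost nothing is lost if compound symmetry turns out to hold.

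### The H2/H3 models leave out the randomized display position, which can cost the arm-by-product contrasts (interaction test, H4, H5) a little precision

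*Combined protocol and SAP*

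**What the plan says.** Study Protocol has each participant see three mock bags of chips "displayed in a random order". It continues: "For each product, participants will rate their purchase intentions, perceived product healthfulness, and indicate whether they believe the product to be ultraprocessed". Each outcome is thus measured three times per person, and display position is set by randomization.

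Main Analyses specifies the linear models for H2 and H3 as follows: "Models will regress each outcome on indicator variables for experimental arm, indicator variables for product, and their interactions". The only other element is the participant effect: "Models will include random intercepts to account for repeated measures within participants". The joint test of the interaction terms then decides whether the label effect is reported by product or pooled. The logistic model for H1 has the same fixed effects: "The model will regress identification of products as UPFs on indicator variables for experimental arm, indicator variables for product, and their interactions". Position is in none of these models, and no check of order effects is described.

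Hypotheses adds H4 and H5, which predict that the label's impact on purchase intentions and perceived healthfulness "will be greater for the product not high in any nutrients of concern than for the products high in one or two nutrients of concern". The arm-by-product terms are the only modelled basis for these two hypotheses.

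**The concern.** Three bags of the same flavor receive the same questions, so ratings may drift with position, for instance through fatigue or through familiarity after the first bag and its questions. With no position term, a mean drift of this kind counts as unexplained variation within participants. Contrasts between products within a person are judged against exactly that variation.

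What is at stake is precision in three places: the interaction test that decides what is reported for the continuous outcomes, H4, and H5. The sample cannot be enlarged to compensate, since it was set elsewhere: "The total sample of 3,300 size was calculated based on the primary outcomes of the parent study".

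**Working it through.** The plan has no figure for position effects or for within-person correlation, so there is nothing of its own to reproduce. The detectable effect in Sample Size and Power does not enter this check.

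**Inputs from the documents:** three ratings per participant in random order; N = 3,300, hence 3 × 3,300 = 9,900 ratings per outcome before exclusions; fixed effects and random intercept as described above.

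**Assumed inputs:** SD of 1 apart from position; ICC ρ of 0.5 to 0.7; linear position effects −d, 0, +d with d = 0.1, 0.2 or 0.3 SD, the same in both arms; 1:1 allocation (the ratio is not stated, and it does not affect the ratios below).

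**Step 1, H4/H5 contrast.** For each participant take the product with no nutrient of concern minus the mean of the other two.
- Residual variance with position modelled: (1 + 1/4 + 1/4)(1 − ρ) = 1.5(1 − ρ).
- The three position effects sum to zero within a person, so their contribution to the contrast is 1.5 times the effect for the first product. One position effect has variance 2d²/3. The added variance is 2.25 × 2d²/3 = 1.5d².
- Variance ratio, without versus with position: 1 + d²/(1 − ρ). The SE ratio is its square root.

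**Step 2, joint interaction test.** Position effects within a person have variance 2d²/3 and covariance −d²/3, and the difference is d². The within-person residual variance therefore rises from 1 − ρ to 1 − ρ + d², and the Step 1 factor applies to every contrast between products.

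**Step 3, product-specific arm effect.** The SE ratio is √(1 + 2d²/3).

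**Step 4, across-product arm effect.** Each participant's three position effects add to a constant, so the SE ratio is 1.000 when all three ratings are present.

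| d per position | H4/H5 SE ratio, ρ = 0.5 | H4/H5 SE ratio, ρ = 0.7 | Power if 80% with position modelled (ρ = 0.5; 0.7) | Product-specific SE ratio |
|---|---|---|---|---|
| 0.1 | √1.020 = 1.010 | √1.033 = 1.017 | 79%; 79% | 1.003 |
| 0.2 | √1.080 = 1.039 | √1.133 = 1.065 | 77%; 75% | 1.013 |
| 0.3 | √1.180 = 1.086 | √1.300 = 1.140 | 73%; 69% | 1.030 |

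**Step 5, simulation** (2,000 runs per setting, ρ = 0.5, no true label effect, arms compared on participant-level contrasts). Adding position lowered the H4/H5 SE from 0.0304 to 0.0301 at d = 0.1, from 0.0313 to 0.0302 at d = 0.2, and from 0.0328 to 0.0302 at d = 0.3, in line with the formula. Without position, mean estimates were within 0.001 of zero and null rejection of the contrast was 0.049 to 0.053. The SE of the three-product mean did not change.

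**The case against.** The strongest reply is that randomizing order already does what is needed. Estimates are unbiased and tests keep their level, so nothing in the plan is invalid and position is an optional precision covariate. That stands, and it is why the point ranks low.

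The size is also assumed. A shift of 0.3 SD per position is 0.6 SD from first bag to third, nearly four times the only effect size that Sample Size and Power cites from previous work (0.6/0.16 = 3.75, although that figure concerns identification as ultraprocessed). At 0.1 SD the loss is under 2% of the SE. This stands too.

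A reader might infer that position indicators would deal with anchoring or contrast between successive bags. They would not. Those effects depend on which product came before. Under random order any product is as likely to precede another as to follow it, so symmetric shifts average to zero at each position and there is no mean for the indicators to remove. Only a mean shift by position is recovered.

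A reader might also extend the argument to H1. The logistic model has no additive residual, and leaving position out there mainly attenuates the conditional log-odds slightly. The formula above does not apply to it.

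Finally, the documents say only that the experiment is programmed in Qualtrics. They do not say that display order is recorded, so the low cost of the remedy depends on confirming this.

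**Conclusion.** The point holds as a free improvement of low priority. The linear models omit a factor that the design randomizes, and any mean shift by position then adds to the error of the arm-by-product contrasts. The cost to H4/H5 is about 1-2% of the SE at 0.1 SD per position, 4-6% at 0.2 and 9-14% at 0.3, for an ICC of 0.5 to 0.7. Product-specific effects barely change (SE ratio 1.003 to 1.030). The across-product H2/H3 effect does not change for participants with all three ratings.

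These sizes rest on an assumed ICC and an assumed linear shift common to both arms, and the loss is zero if there is no shift. A reader might infer that the omission biases the product comparisons or inflates false positives. The documents do not support that, because display order is randomized.

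**What to change.** In Main Analyses, add fixed-effect indicators for second and third display position to the linear models for purchase intentions and perceived healthfulness. State that they stay in the model whether or not the arm-by-product interactions are dropped. First confirm that the survey records and exports display order for each participant. The same two terms may go into the H1 logistic model for consistency, with no precision gain claimed there.

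The cost is one sentence in the plan, one exported field and two parameters against about 9,900 ratings per outcome. If display order is already recorded, nothing changes for participants.

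### The stated detectable effect of d=0.06 does not follow from the stated inputs: they give d=0.098 for one rating per participant, and 0.06 needs an unstated within-person correlation of about 0.07 or less

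*Combined protocol and SAP*

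**What the plan says.** All places are in the combined protocol and SAP.

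- **Sample Size and Power**: the total of 3,300 was set by the parent study. G*Power 3.1 was then used to find the smallest detectable effect at alpha 0.05, 80% power and 1 degree of freedom, and the result is that "we would be able to detect an effect of $d=0.06$ or larger". The sample is judged sufficient because in an earlier study with similar labels "we found an effect size of $d=0.16$ on correct identification of products as UPF".
- **Study Protocol**: "participants will be randomly assigned into 1 of 2 arms". Three products are shown to everyone, and "For each product, participants will rate their purchase intentions", along with healthfulness and whether the product is ultraprocessed.
- **Main Analyses**: "We will use a two-sided critical alpha of 0.05 to conduct all statistical tests". The models carry participant random intercepts for the repeated ratings. For the continuous outcomes, "If the interactions are jointly significant, we will keep them in the model" and the label effect is given product by product; otherwise one effect across products is reported.
- **Hypotheses**: correct identification (H1) and purchase intentions (H2) are co-primary. H4 predicts that the label's effect on purchase intentions "will be greater for the product not high in any nutrients of concern" than for the other two.
- **Exclusions and Outliers**: "We will exclude participants who complete the survey implausibly quickly", and also those who finish less than 90% of the survey. No expected loss is given.

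The plan does not state the G*Power procedure, the allocation ratio, the number of measurements used, or a within-person correlation.

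**The concern.** A standardised difference of 0.06 between two independent groups is very small, and 1,650 per group looked too few to detect it with 80% power. The three ratings per person could narrow the gap. But they come from the same person judging three bags of chips of one flavour, and the analysis itself models dependence between them. How much the repetition helps depends on a correlation that the plan never gives.

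At stake is how H2 is read. The d=0.16 argument concerns correct identification only, and no reference effect is offered for purchase intentions (nor for healthfulness, H3). The 0.06 is therefore the only figure from which a reader can judge what a null result on purchase intentions would rule out. If it is too optimistic, such a result would be over-interpreted.

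**Working it through.** **Inputs.** From Sample Size and Power: N=3,300, alpha 0.05, power 80%, 1 df. From Study Protocol: two arms, three ratings per participant. From Main Analyses: two-sided tests. Assumed: 1:1 allocation, so 1,650 per arm (any other ratio makes the detectable effect larger; 2:1 gives 0.103). Effects are in units of the standard deviation of a single rating.

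**Step 1: try to reproduce 0.06 with one rating each.**

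d = (z₀.₉₇₅ + z₀.₈₀) × √(2/1650) = (1.960 + 0.842) × 0.0348 = 0.0975 (0.0976 with the noncentral t).

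Other readings:

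| Reading | Result |
|---|---|
| One-sided alpha 0.05 | d = 0.087 |
| 3,300 per arm instead of in total | d = 0.069 |
| 1-df effect size w or f | 0.049 (f=0.049 is d=0.098) |
| 9,900 ratings counted as independent | d = 0.056 |

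Only the last rounds to 0.06. It is one possible source, but the plan does not say so. Reading 0.06 as w would mean changing a stated input: w is 0.056 at 90% power, 0.063 at 95%, or 0.057 with 3 df. In any case w is not d.

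**Step 2: allow for three ratings per person.** With a common within-person correlation ICC,

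d = 0.0975 × √((1 + 2·ICC)/3).

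Setting d=0.060 and solving: ICC = [3 × (0.060/0.0975)² − 1]/2 = 0.068. With d=0.065, the largest value that could round to 0.06, ICC = 0.166.

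**Step 3: size of the gap.** Power at d=0.06 is Φ(0.06/SE − 1.960), with SE = 0.0348 × √((1 + 2·ICC)/3). The ICC values are assumptions.

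| ICC | Detectable d, averaged over products | Power at d=0.06 |
|---|---|---|
| 0 | 0.056 | 85% |
| 0.2 | 0.067 | 71% |
| 0.3 | 0.071 | 66% |
| 0.4 | 0.076 | 60% |
| 0.5 | 0.080 | 56% |
| 0.7 | 0.087 | 49% |
| Single product | 0.098 | 41% |

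The last row applies when the interactions are jointly significant and effects are reported by product, because each such effect rests on one rating per person.

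For scale only, 80% power at d=0.06 would take about 4,650 participants at ICC 0.3, 5,820 at ICC 0.5, and 8,720 with one rating each.

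**Step 4: exclusions.** If 10% were excluded (assumption; N=2,970), the detectable effect is 0.075 at ICC 0.3, 0.084 at ICC 0.5 and 0.103 for a single product.

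**Step 5: H1.** Power at d=0.16 with one rating each: Φ(0.16/0.0348 − 1.960) = 99.6%. It is 99.2% after an assumed 10% exclusion and 98.4% after 20%. A lower ICC with three ratings only raises these.

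**The case against.** Four points can be made for the plan.

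1. **Other routes reach 0.06.** A 1-df arm-by-product contrast (the product with no nutrient warning against the mean of the other two) has detectable effect 0.0975 × √(1.5 × (1 − ICC)), which is 0.060 at ICC 0.75. One-sided alpha with three ratings gives 0.060 at ICC 0.22 and 0.065 at ICC 0.35. Neither rescues the figure. The contrast answers the moderation question, whereas the plan sets 0.06 beside an effect of the label itself. One-sided testing contradicts Main Analyses. Both also need a correlation that the plan does not give. What stands is that the 0.07 limit is specific to the two-sided arm effect averaged over three products, and that rounding stretches it to 0.17.

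2. **H4 need not lead to product-level reporting.** H4 is directional, while the reporting rule depends on a joint interaction test that could miss a true difference. This stands: the 0.098 figure is conditional on that test.

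3. **The practical consequence is limited.** The sample was fixed by the parent study, the one adequacy argument offered (d=0.16 for H1) survives, and no expected effect for H2 is stated against which it could be called underpowered. This stands too. It limits the remedy to a corrected statement, but does not make 0.06 right.

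4. **The H1 check has its own assumptions.** It takes the earlier d=0.16 to be on the scale of a single rating, and uses a comparison of means in place of the logistic mixed model. Both caveats are fair.

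**Conclusion.** The point holds. The stated d=0.06 cannot be obtained from the stated inputs without a near-zero within-person correlation that the plan neither states nor supports. For the effect averaged over products, the detectable difference is 0.071 to 0.087 over assumed ICCs of 0.3 to 0.7. For one product it is 0.098, about 1.6 times the stated value (0.098/0.06). These figures rest on 1:1 allocation, a common correlation among the three ratings, and all 3,300 being analysed; unequal allocation or exclusions make them larger.

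The conclusion that the sample is adequate for correct identification is not disturbed, subject to the scale and model caveats above. The sensitivity claim for purchase intentions is. It should be corrected, because no other figure in the plan speaks to that co-primary outcome.

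**What to change.** In Sample Size and Power:

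- Name the G*Power procedure, the number of measurements and the assumed ICC, and replace 0.06 with the value recomputed for that ICC.
- If no ICC estimate exists, give a range labelled as an assumption, for example:

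> With 3,300 participants allocated 1:1, two-sided alpha 0.05 and 80% power, the detectable effect averaged over the three products is d=0.071, 0.080 and 0.087 at assumed within-person correlations of 0.3, 0.5 and 0.7. It is about 0.098 for a single-product effect, which is reported if the interactions are jointly significant.

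- State the allocation ratio, and whether 3,300 is counted before or after the exclusions.
- State that the d=0.16 comparison supports H1 only, and that the sensitivity for H2 is the restated figure.

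The cost is a few rewritten sentences and a less favourable number, unless the sponsor can support an ICC of about 0.07 or less (0.17 with rounding). No extra participants and no change to the analysis are needed.
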